volume multiplied by ventilatory frequency) and expiratory tidal volume. In both groups of patients Com_{dyn} will be measured after delivery, but before RM (baseline measurement), and then 3, 10 and 20 minutes after the RM. At the same time points arterial blood pressure (systolic, diastolic and mean), heart rate, SpO₂, blood gas, ETCO₂, P_{peak}, expiratory tidal volume and minute volume will be measured too. SpO₂ and blood gas will be also measured postoperatively (10 minutes after extubation). Tables 2 and 3 present the basic patient's measurements. Data analysis example comes from preliminary data analysis before the beginning of the study.

Follow up measurements

Patients will be followed up for postoperative respiratory failure, which is defined as the need for non-invasive ventilation and/or mechanical ventilation after extubation. In cases of respiratory failure, the possible pulmonary complications are also being defined: pneumonia, atelectasis, pulmonary embolism, pneumothorax, acute lung injury (ALI), asthma, non-cardiogenic pulmonary oedema and severe hypercapnia. The routine postoperative oxygen use will also be noted and will be applied for half an hour postoperatively.

Statistical analysis

Before the beginning of the study, and for **determination of sample size**, we will conduct **power analysis**, in an attempt to estimate the sample size required so that the study would have adequate power to detect clinically meaningful differences between the two study groups with regards to lung compliance (dv/dp), which is the primary outcome of the study. For this analysis, we used the G*Power Software that is freely available online at <http://www.gpower.hhu.de/en.html> from the Psychology Department of the University of Dusseldorf, in Germany.

Our power analysis is based on previous studies but is even more generous^{17,22}. The required sample size calculation was based on the following assumptions: Clinically meaningful difference between the two groups is 20% of the mean value, and SD of the observed lung compliance is 25% of the mean value (rather generous), therefore size effect $d = 20\% / 25\% = 0.8$, with two-sided testing, with $\alpha = 0.05$ and $b = 0.1$ (therefore, power = $1 - b = 0.9$). Under these assumptions, G*Power indicated that we will need minimum 34 patients per group for this study to have adequate power. To confirm accuracy of this calculation, we will also conduct sample size estimation using the Statistica v 7.0 Statistical Software package (StatSoft Inc, Tulsa, Oklahome, USA), in order to find out if this confirmatory analysis will produce identical results. Finally we will confirm our results using the suitable mathematic formula (see [appendix 2](#)).

In order to allow for possible protocol violations, errors, patient attrition or other study shortcomings, we will enroll 45 patients in each arm of the study (about 10 women more in each group of patients). As pregnant women are a very “sensitive” population and we are afraid of much protocol violation (removal women from protocol mainly due to hemodynamic instability) we will chose to randomize 45 women per group, which is a generous number.

We will check if data are normally distributed (Kolmogorov Smirnov and Shapiro Wilks test). Ventilatory and haemodynamic data and intraoperative and postoperative variables (all continuous variables) will be presented as mean values (+/- SD). Data will be compared between and within groups using Mixed Analysis of Variance (Mixed Anova-General Linear Model) if are normally distributed or with Kruskal Wallis test in case that we do not have normally distributed data.

Bonferoni correction will be used for multiple comparisons correction. In order to check and supplement our Mixed Analysis of Variance we will also use two-sample t-test to compare the two groups at each time point (for ventilatory and haemodynamic variables). Patient and procedural characteristics will be compared between groups using chi-square test for categorical variables and independent-sample t-test for continuous variables. Two tailed P-values <0.05 will be considered statistically significant. For data analysis SPSS statistical software version 22 will be used.

Patients Records

For each patient we will have four data files:

1. Demographic intra- and post-operative patient data (appendix 3)
2. Mechanical ventilation data (appendix 4)
3. Haemodynamic data (appendix 5)
4. Blood gas data (appendix 6)

Data Presentation Plan

Number of eligible women and number of women excluded before randomization (lets say X):

Possible reasons for exclusion:

[figure not shown]
X1 women could decline participation and choose regional anesthesia, X2 could have emergency surgery, X3 will have active asthma, X4 will have BMI >40, X4 will be < 18 years old, X5 will suffer arterial hypertension etc. If we add: $X1+X2+X3+X4+X5+... Xi=X$

Finally we will include 45 patients in each group.

Number of women that will complete the study = F (For example 40 women in the RM group and 41 women in the Control group)

Give reasons for not complete the study: Heart rate >110bpm, Low arterial blood pressure, hypertension, asthmatic attack during the surgical procedure etc.

Flow chart:

If all, or almost all of the patients will complete the study (we will have the most of the measurements in each time point) we will use a per protocol analysis. If we have many missing data we will use an intention to treat analysis of data (ITT). According to ITT analysis of data I will use all the data of all the randomized patients regardless of whether they completed the trial or not. For the missing values I will use the “last observation carried forward” (LOCF) approach

Patient characteristics should be similar between the two groups (table 1). If not we will have to mention the differences and this would be a serious limitation of our study.

Intraoperative characteristics (time to delivery, anesthesia duration, estimated blood lose, administration of crystalloids and/or colloids, administration of blood products and intraoperative use of ephedrine should be similar between the two groups (table 1).

The length of hospital stay and the possible differences between the two groups should be mentioned (table 1). The number of patients that will suffer postoperative pulmonary complications (mainly pneumonia, diagnosed with chest radiogram and clinical evaluation) and possible differences between the two groups should also be mentioned. Pneumothorax would be a serious adverse event, which could have a strong relationship with the RM manipulation of the patients and should be recorded. See adverse event section below.

Table 1: Patient characteristics presented as mean (SD) or n=number of patients. Intra- and post-operative characteristics presented as mean (SD).

Patient Characteristics	RM Group n=45	Control Group n=45
Age (yrs.) [mean (SD)]	A1	B1
BMI (kg/m ²) [mean (SD)]	A2	B2
Smoking status (n)	A3	B3
Intraoperative Characteristics		
Duration of anesthesia (min)	A4	B4
Time to delivery (min)	A5	B5
Crystalloids (ml)	A6	B6
Colloids (ml)	A7	B7
Blood (units)*	A8	B8
Ephedrine dose (mg) ⁺	A9	B9
Postoperative Characteristics		
Length of hospital stay (days)	A10	B10
Pulmonary complications (n)	A11	B11
Pneumothorax (n)	A12	B12
Pneumonia (n)	A13	B13
Other (n)	A14	B14

Efficacy and Safety issues:

The efficacy of the RM to improve lung compliance and gas exchange will be the main efficacy issues of the study. The investigators believe that the Com_{dyn} (dv/dp) will be statistical significantly improved in the RM group compared to the control group (statistical significant difference between groups). A 20% increase in mean Com_{dyn} in the RM group compared to the control group would be clinically significant. This change in lung compliance perhaps would not have any significant impact for the majority of the patients of our study (young and healthy patients). However, underlying comorbidities may amplify changes in lung and cardiovascular physiology and anaesthesia may serve as a 'second-hit' that worsens patient outcome. For this reason a RM and the application of protective lung ventilation (low tidal volumes and PEEP) perhaps should be the suitable anesthetic practice for all the patients.

The investigators also believe that there would be statistical significant difference within groups too. In the RM group possibly there would be a difference in lung compliance (increase) between baseline and all the other time points (3, 10 and 20 minutes after the RM). Again a 20% increase in Com_{dyn} would be clinically significant, at least for some patients.

The investigators believe that the recruitment manoeuvre will improve the intraoperative and/or postoperative PO_2 , the PO_2/FiO_2 and the SpO_2 . Again for the population of our study (all women have a baseline $PO_2/FiO_2 > 400$) this improvement will not have a significant impact. All the data will be presented in tables 2 and 3 (**see next example with preliminary data analysis**).

Because of the higher inspiratory pressures during RM and PEEP used, the $P_{plateau}$ and P_{peak} are anticipated to be significantly higher in the RM group, compared with those in the control group, and this would be a possible serious safety issue, as high alveolar pressures could result in pneumothorax or/and barotrauma. As the study involves young and healthy population, the investigators believe that the above safety issues will not be a serious problem of the study. A second safety issue will be the hemodynamic instability during RM. Patients with serious hemodynamic instability will be removed from the study, as already mentioned.

End of treatment

The treatment (RM) will start after delivery (3 minutes) and will last until the end of the surgery. Specifically, in the RM group the RM will be performed 3 minutes after delivery but PEEP and low tidal volume (which are part of the whole RM technique) will be continued until the end of the operation.

End of Study

The patients will be monitored throughout the operation and in the postoperative period too (see also the measurements section-primary end point, secondary measurements and follow up). The follow up will last for all the length of hospital stay. The length of hospital stay will be recorded while all the adverse events that will be occurred during this period they will be recorded too. For this kind of population the hospital stay is usually short (<5 days).

Adverse events:

Hemodynamic instability during the RM will be the most important adverse event of the study. During the RM all women should be closely monitored for the occurrence of hypotension or the administration of a fluid bolus or vasopressor medication to support haemodynamic variables. Of course during the whole course of anesthesia the need for vasopressor should be monitored. Possible differences between the two groups should be mentioned for all the above parameters (table 1).

Postoperative lung complications (pneumonia, atelectasis, pulmonary embolism, pneumothorax, acute lung injury (ALI), asthma, non-cardiogenic pulmonary oedema and severe hypercapnia) should also be recorded. As we will mainly include young and healthy population serious lung complications and differences between groups are not anticipated.

Preliminary Data Results

For safety issues we decided to perform a preliminary data analysis before the beginning of the study. We used 7 patients in each group, and we will use these data analysis as an example of our data presentation plan and to show the most important measurements of our study. At all time points (3, 10 and 20 minutes) after intervention there is a significant difference in Com_{dyn} between the two groups ($p < 0.001$). The Com_{dyn} is much higher in the RM group vs control group (table 2). The significant difference in lung Com_{dyn} depicts in figure 1a too.

Post intervention the peak inspiratory pressure at all time points (3, 10 and 20 minutes) is significantly lower in the RM group compared to control group ($p = 0.021$, table 2, figure 1b).

PO_2/F_iO_2 and PO_2 are also significantly higher in the RM group vs the control group ($p < 0.001$) at all time points post intervention (3, 10 and 20 minutes) while PO_2 is also significantly higher in the RM vs control group postoperatively ($p < 0.001$). SpO_2 is significantly difference between the two groups at 10 and 20 minutes post intervention and postoperatively ($p = 0.04$) – table 2

There are no significant differences in expiratory tidal volume, minute volume, end tidal CO_2 , PCO_2 and in hemodynamic data between the two groups (tables 2, 3).

[figure not shown]
Table 2. Respiratory Mechanics and Gas Exchange in the two groups of pregnant women (recruitment vs control, respectively-**Example**). Data are presented as mean \pm SD. The P-value corresponds to the tests of between subject main effects using the mixed Anova test (recruitment vs control group). The two groups were also compared separately at each time point using the independent two-sample t-test (*) and (**). (*) denotes significant differences from the control when $P < 0.01$ while (**) is used whenever $P < 0.05$. PaO₂, arterial blood oxygen; PaCO₂, arterial blood CO₂; SpO₂, arterial blood oxygen saturation; FiO₂, oxygen concentration.

	Baseline	After intervention (minutes)			Postoperative	P-value
		3 min	10 min	20 min		
Peak Inspiratory Pressure (cmH₂O)					-	0.021
Recruitment	23.9 (2.9)	19.9 (2.5)*	20.2 (2.9)*	20.3 (3.0)*		
Control	23.0 (2.8)	22.1 (2.8)	22.5 (2.7)	22.2 (2.7)		
Com_{dyn} (ml/cmH₂O)					-	<0.001
Recruitment	33.6 (6.8)	51.4 (12.8)*	49.9 (11.2)*	49.7 (10.9)*		
Control	31.1 (7.9)	29.6 (7.2)	30.6 (8.1)	30.9 (8.1)		
PaO₂ (mmHg)						<0.001
Recruitment	211.7 (10.6)	242.7 (26.9)*	242.1 (22.0)*	243.5 (27.6)*	108.4 (6.7)*	
Control	214 (18.4)	219.8 (22.6)	214 (22.3)	212 (38.4)	98.4 (5.3)	
PaO₂/FiO₂					-	<0.001
Recruitment	422.2 (22.1)	481.1 (48.6)*	475.3 (42.7)*	474 (50.3)*		
Control	426.4 (43.3)	429 (39.2)	426 (41.5)	422.5 (37.5)		
ET_{CO2} (mmHg)					-	0.5
Recruitment	30.9 (3.4)	29.2 (3.4)	28.4 (3.8)	28.1 (3.6)		
Control	30.4 (2.9)	30.0 (3.0)	29.4 (2.8)	28.6 (2.7)		
Expiratory Tidal Volume (ml)						0.5
Recruitment	584.5 (63.1)	588 (65.3)	578 (66.2)	581 (65.1)	576 (62.8)	
Control	575.9 (54.2)	582 (66.3)	585 (58.4)	579 (66.3)	585 (64.8)	
Minute Volume (lit)						0.38
Recruitment	7.0 (7.74)	7.1 (0.63)	6.9 (0.65)	7.1 (0.68)	6.9 (0.65)	
Control	6.8 (0.63)	6.9(0.67)	6.8 (0.72)	7.1 (0.65)	6.8 (0.59)	
PCO₂ (mmHg)						0.08
Recruitment	33.9 (2.2)	32.7 (3.0)	32.7(3.8)	32.7 (3.7)	35.6 (1.9)**	
Control	34.4 (1.9)	33.7 (2.9)	33.8 (2.9)	33.6 (3.2)	36.5 (1.4)**	
SpO₂						0.04
Recruitment	98.8 (0.7)	99 (0.7)	99.1 (0.8)**	98.9 (0.8)**	98.3 (0.8)*	
Control	99 (0.7)	98.9 (0.7)	98.7 (0.6)	98.6 (0.5)	97.7 (0.7)	

Table 3. Systolic Arterial Pressure, Diastolic Arterial Pressure, Mean Arterial Pressure and Heart rate between the two groups of pregnant women (recruitment vs control, n=40 and n=41 respectively- **Example**). Data are presented as mean \pm SD. The P-value corresponds to the tests of between subject main effects using the mixed Anova test (recruitment vs control group). The two groups were also compared separately at each time point using the independent two-sample t-test.

	Baseline	After Intervention (minutes)			P- Value
		3 min	10 min	20 min	
Systolic Arterial Pressure (mmHg)					0.63
Recruitment Control	124.5 (6.2) 125.7 (9.1)	121.8 (8.4) 122.7 (9.5)	122.8 (9.8) 120.1 (10.7)	121.9 (10) 119.2 (10.5)	
Diastolic Arterial Pressure (mmHg)					0.8
Recruitment Control	73.6 (10.5) 72.7 (8.0)	70.5 (10.0) 70.6 (7.6)	70.3 (9.6) 71.1 (7.6)	69.6 (9.0) 71.1 (6.3)	
Mean Arterial Pressure (mmHg)					0.98
Recruitment Control	88.8 (10.20) 88.4 (9.50)	83.4 (10.1) 85.8 (7.4)	84.4 (10.3) 83.8 (7.2)	83.8 (10.3) 82.4 (7.2)	
Heart Rate (beats per minute)					0.96
Recruitment Control	95.1 (12.3) 96.2 (6.7)	92.5 (12.4) 91.6 (6.2)	91.6 (11.6) 91.5 (6.6)	91.4 (12.0) 91.0 (7.0)	

Figure 1a and 1b: RM=recruitment maneuver group, Baseline=before intervention, 3, 10 and 20 minutes=post intervention time.

Difference in Peak Inspiratory Pressure between the two groups

[figure not shown]
[figure not shown]

Figure 2:

Difference in PO₂/FiO₂ ratio between the two groups

Discussion:

Lung-protective ventilation, which refers to the use of low tidal volumes PEEP, and which may also include the use of RM, has been shown to reduce mortality among patients with the acute respiratory distress syndrome and is now considered best practice caring of many critically ill patients^{2,9,15,19,23,24}. Over the last years many physicians have questioned the benefits of using lung-protective ventilation in the surgical setting, and in many surgical procedures the results are very positive^{2,9,15-18,22,25-31}.

Previous studies

In a recent multicenter, double-blind, parallel-group trial with 400 patients the investigator concluded that as compared with a practice of nonprotective mechanical ventilation, the use of a lung-protective ventilation strategy in intermediate-risk and high-risk patients undergoing major abdominal surgery was associated with improved clinical outcomes and reduced health care utilization². In this trial the primary outcome was a composite of major pulmonary and extra-pulmonary complications occurring within the first 7 days after surgery. In a systematic review published in 2014 the investigators developed the benefits of lung protective ventilation during surgery and general anesthesia and offers some recommendations (Lung-protective ventilation, which refers to the use of lower tidal volume and limited Pplateau to minimize overdistension, and PEEP to prevent alveolar collapse at end-expiration) for mechanical ventilation in the surgical context⁹. In another systematic review and meta-analysis which published in 2012 the investigators concluded that although the ideal intraoperative ventilation strategy in obese patients remains obscure there is some evidence that RM added to PEEP compared with PEEP alone improves intraoperative oxygenation and compliance without adverse effects. There was no evidence of any difference between PCV and VCV¹⁶. In three other prospective clinical trials the RM proved very effective in restoration of lung compliance and lung mechanics in laparoscopic surgery^{15,17,18} while one more study in normal weight and obese patients undergoing laparoscopic surgery had the same beneficial results²². One more study published in 2012 showed ventilation improvement during thoracic surgery³⁰ while RM strategy improved arterial oxygenation after cardiopulmonary bypass too²⁵. In 2010 Tusman et al. insisted that the application of RMs during anaesthesia normalizes lung function along the intraoperative period and that there is physiological evidence that patients of all ages and any kind of surgery benefit from such an active intervention²⁹.

Atelectasis is the main cause of postoperative pulmonary complication while the danger is mainly noted in high-risk patients^{1,3}. Pregnant women are considered “healthy women” and low risk for GA, but on the other hand mimic they obese patients. This will be the first study, where it will be perform RM in this special population.

Limitations of the study

In our study we will check for differences in Com_{dyn} but not in the static compliance, which is also a very important record of the pulmonary performance. The reason is the lack of the special instruments. Many other records could be performed for respiratory mechanics too.

As we will use both RM and PEEP we will not be able to know if the compliance increasement (if exist) will be due to RM or to PEEP.

While this study will probably demonstrate a restoration in pulmonary compliance and in oxygenation, it will not be powered to describe pulmonary outcomes, such as postoperative atelectasis or pneumonia.

Appendix 1

Clinical Trial Methodology, [name]

Permuted blocks:

We consider a block of 10 patients and two treatments RM and Control. Then we define an array of 10 numbers, from 1 to 10:

1 2 3 4 5 6 7 8 9 10

A permutation of the array may produce the following blocks:

Block 1: 3 5 1 4 9 8 10 2 6 7

Block 2: 1 6 8 9 10 2 4 5 7 3

Block 9: 4 7 9 2 8 10 6 1 3 5

We need 9 blocks (90 patients)

We assign digits 1-5 to A

Digits 6-10 to B

Block	Sequence	Treatment	Patients
Block 1	3	A	1
	5	A	2
	1	A	3
	4	A	4
	9	B	5
	8	B	6
	10	B	7
	2	A	8
	6	B	9
	7	B	10
Block 2	1	A	11
	6	B	12
	8	B	13
	9	B	14
	10	B	15
	2	A	16
	4	A	17
	5	A	18
	7	B	19
	3	A	20
Block 3	3	A	21
	1	A	22
	7	B	23
	9	B	24
	2	A	25
	4	A	26
	10	B	27
	8	B	28
	5	A	29
	6	B	30

Διπλωματική Εργασία – [name]

Block 4	9	B	31
	3	A	32
	2	A	33
	10	B	34
	7	B	35
	1	A	36
	4	A	37
	8	B	38
	5	A	39
	6	B	40
Block 5	5	A	41
	1	A	42
	9	B	43
	7	B	44
	2	A	45
	10	B	46
	3	A	47
	4	A	48
	6	B	49
	8	B	50
Block 6	9	B	51
	1	A	52
	3	A	53
	7	B	54
	2	A	55
	4	A	56
	5	A	57
	8	B	58
	10	B	59
	6	B	60
Block 7	10	B	61
	5	A	62
	1	A	63
	8	B	64
	3	A	65
	2	A	66
	9	B	67
	4	A	68
	6	B	69
	7	B	70
Block 8	3	A	71
	8	B	72
	10	B	73
	1	A	74
	9	B	75
	2	A	76
	7	B	77
	6	B	78
	4	A	79
	5	A	80
Block 9	7	B	81
	1	A	82
	4	A	83
	8	B	84
	3	A	85
	10	B	86
	2	A	87
5	A	88	

	9	B	89
	6	B	90

Appendix 2

We will use power analysis – Two independent groups (comparison of means)-Clinical Trial Methodology, [name]

- Sample size in two independent groups.
- The formula for calculating the sample size is: $n \geq 2 \left(\frac{s}{\Delta} \right)^2 (1.96 + 1.28)^2$
- $S = SD$ (from previous trials it was found that the between subject variance of compliance is 25)
- $\Delta = 20$ (difference in compliance that is considered clinically significant)

Consequently,

$$*n \geq 2 \left(\frac{25}{20} \right)^2 (1.96 + 1.28)^2 \rightarrow n \geq 33 \text{ patients on each group}$$

*If we include +10% to compensate for potential loss then the final sample size should be at least 37 patients on each group

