Before induction of anesthesia preoxygenation (100% oxygen via face mask) for 2 minutes will be conducted to all the patients. After tracheal intubation, pregnant women in both groups will be mechanically ventilated (Datex-Ohmeda, Aestiva/5, Madison, WI, USA) with volume-controlled mode and with tidal volume at 8-ml/kg ideal body weights. Inspiratory to expiratory time ratio will be set to 1:2 while 40% oxygen fraction (balanced with air) will be used. The respiratory rate will be adjusted to maintain an end-tidal CO₂ between 30-35 mmHg and zero end-expiratory pressure will be applied (ZEEP). Immediately after delivery the control group of women will continue with exactly the same ventilator management while in the RM group lung recruitment will be achieved as follows:

[figure not shown]
The ventilator will be switched to pressure-controlled mode and the inspiratory time will be increased to 50% (inspiratory /expiratory ratio will be set to 1:1). The Peak inspiratory pressure (P_{peak}) will firstly be set to 20 cmH₂O (for 3 breaths) and then the investigators progressively will increase the positive end-expiratory pressure (PEEP) to have a P_{peak} up to 45-50 cmH₂O. The PEEP sequential will increase in four steps from 0 to 5 cmH₂O (for 3 breaths), from 5 to 10 cmH₂O (for 5 breaths), from 10 to 15 cmH₂O (for 7 breaths) and from 15 to 20 cmH₂O (for 10 breaths). The whole RM will last about 2 minutes. After the RM the investigators will use volume control ventilation again with the baseline settings mentioned above, tidal volume 6ml/kg and PEEP step-wise decrease to 8 cmH₂O, which must be maintained until the end of the operation. Lung recruitment in the RM group will not be repeated, as cesarean section is a short lasting operation. After completion of the operation and neuromuscular block reversal women in both groups will breath spontaneously before tracheal extubation and PEEP will be eliminated in the RM group. Also see flowchart below:

Study Design – Ventilatory Management Flowchart

RM Group

Control Group

Blinding procedure

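### In the per-protocol branch, the named mixed ANOVA drops a woman with one missing reading from that variable's overall tests, although her other readings exist.

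*Protocol*

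**What the plan says.** The Statistical analysis section compares normally distributed ventilatory and haemodynamic data between and within groups by "Mixed Analysis of Variance (Mixed Anova-General Linear Model"; the software is also fixed: "For data analysis SPSS statistical software version 22 will be used". Two-sample t-tests at each time point are added as a supplement. The legend of the example Table 2 shows what the main analysis reports: "The P-value corresponds to the tests of between subject main effects using the mixed Anova test".

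Each woman has four intraoperative readings of dynamic compliance, the primary endpoint. Under Secondary measurements they are listed as the "baseline measurement), and then 3, 10 and 20 minutes after the RM".

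The Data Presentation Plan then sets two branches. If all or nearly all women complete, described as "we will have the most of the measurements in each time point) we will use a per protocol analysis", the per-protocol route applies. Otherwise: "If we have many missing data we will use an intention to treat analysis of data (ITT"). The LOCF rule comes directly after the description of the ITT analysis. No rule is given for a missing reading in the per-protocol branch.

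**The concern.** A repeated-measures General Linear Model takes one row per woman and needs every within-woman cell filled. One empty cell removes the woman from the analysis of that variable. The protocol does not state this; it follows from the method it names.

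The per-protocol branch explicitly tolerates some gaps and has no rule for filling them. The result is odd. A woman with one missing reading is dropped when few other women have gaps, but kept by LOCF when many do, so her inclusion depends on other women's data.

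Two things are at stake.

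- **Who is excluded.** The Statistical analysis section expects losses mainly from hemodynamic instability. The Adverse events section calls instability during the recruitment manoeuvre the most important adverse event. Exclusion may therefore be related to treatment.
- **Which women each result describes.** The overall test, the t-test at each time, and the tests of different variables could each rest on a different set of women.

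**Working it through.** **1. The protocol's own figure.** Inputs from Statistical analysis: difference 20% of the mean, SD 25% of the mean, so d = 20/25 = 0.8; two-sided alpha 0.05; power 0.90. The noncentral t, with df = 2n − 2 and noncentrality 0.8·√(n/2), gives n = 34 per group with power 0.9015 (n = 33 gives 0.893). The Appendix 2 formula gives 2 × (25/20)² × (1.96 + 1.28)² = 32.8, so 33. Both stated figures reproduce. Enrolment is 45 per arm, with power 0.964 if nothing is lost.

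**2. Women kept by a complete-row analysis.** The documents give no missing rate per reading, so the rate m is an assumption, taken as independent across the four readings. The share of complete rows is (1 − m)⁴. Power uses the same two-sample calculation. The second starting point, 40.5 per arm, is the average of the 40 and 41 completers that the Data Presentation Plan gives as an example.

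| m | (1 − m)⁴ | from 45: n per arm, power | from 40.5: n per arm, power |
|---|---|---|---|
| 1% | 0.961 | 43.2, 0.957 | 38.9, 0.936 |
| 2% | 0.922 | 41.5, 0.950 | 37.4, 0.927 |
| 3% | 0.885 | 39.8, 0.941 | 35.9, 0.916 |
| 5% | 0.815 | 36.7, 0.922 | 33.0, 0.893 |
| 10% | 0.656 | 29.5, 0.856 | 26.6, 0.816 |

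The analysed number falls below 34 when m exceeds 1 − (34/45)^(1/4) = 6.8% from 45 per arm, or 1 − (34/40.5)^(1/4) = 4.3% from 40.5.

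**3. Which rows belong to this branch.** The per-protocol route requires nearly all women to complete. At 10% per reading, 1 − 0.656 = 34% of women have an incomplete row. That is many missing data, and the plan would send it to ITT with LOCF, where no row is dropped. At 5%, 18.5% are incomplete, which already strains the condition. At 1–5% from 45 per arm, power stays between 0.92 and 0.96.

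**4. A clustered pattern.** If 10% of women miss only the 20-minute reading, 45 × 0.90 = 40.5 per arm remain. Power at 40 and 41 is 0.945.

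**5. Precision against a mixed model.** A small simulation used 150 runs per setting, 90 women, SD 25, a difference of 20 after intervention, and readings missing at random.

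- At 5% missing, complete rows kept about 73 women and the mixed model used all 90.
- The SD of the estimated difference was then 5.0 against 4.3 at within-woman correlation 0.5, and 5.1 against 4.7 at 0.8.
- At 2% missing, the two were nearly equal.

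With 150 runs, each SD carries an error of about 1/√300 = 6%. As a cross-check, losing 18.5% of women raises the standard error by a factor of about √(1/0.8145) = 1.11.

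**The case against.** The strongest case on the other side is that little is lost. This branch applies only when few data are missing, 45 women per arm are enrolled against a required 34 precisely to absorb such losses, and compliance is recorded automatically by the monitor in anaesthetised women, so scattered gaps should be few. That stands, and it limits the point: power is not the main argument.

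Some stronger readings are tempting but not supported.

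- **Power falls to 0.86.** A reader might infer this from the 10% row. That much loss would trigger the ITT branch.
- **Women vanish from the 3- and 10-minute group comparisons.** They need not. Those comparisons are two-sample t-tests, which can use every reading available at the time. The readings are lost from the overall between-group and within-group tests.
- **The protocol expects 20-minute readings to be lost.** The remark that "cesarean section is a short lasting operation" explains why recruitment is not repeated. It does not say that readings will be missed.
- **The issue is independent of the per-protocol/ITT rule.** The remedy replaces that rule. A mixed model confined to the per-protocol set would recover only isolated gaps, not women whom the set itself excludes.

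It can also be argued that LOCF was meant for both branches, in which case nobody would be dropped. The sentence is not expressly limited, but its place straight after the ITT description makes that the less likely reading.

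**Conclusion.** The point holds as a moderate one that should be corrected. In the per-protocol branch, the method named for the main analysis discards all readings of a variable from any woman who lacks one of them, while the supplementary t-tests may keep her.

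The cost in precision is modest: power of about 0.95 at 2% and 0.92 at 5% loss per reading from 45 per arm. It dips to 0.89 only if 5% is lost on top of the example attrition to about 40.5 per arm, a pessimistic combination because completers should have few gaps. What carries the point is possible non-random exclusion, and main and supplementary results that describe different women.

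This rests on three assumptions: the analysis is the usual repeated-measures GLM with one row per woman; LOCF belongs to the ITT branch only; and the missing rates, with independence between readings, are as assumed here. The documents do not show how many readings will be missing or that missingness will differ between arms, so no size of bias can be given.

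**What to change.** In Statistical analysis, replace the GLM mixed ANOVA by a linear mixed model fitted by REML (the MIXED procedure of the SPSS version already named). Include group, time as a category, and group-by-time, with an unstructured within-woman covariance. Fit it to all randomised women with at least one post-intervention reading, in the group to which they were randomised, using every observed reading and imputing nothing. State which contrast from this model replaces the main-effect P-value in Table 2, and take the group differences at 3, 10 and 20 minutes from the same model so that all results for a variable describe the same women.

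In the Data Presentation Plan, delete the per-protocol/ITT switch and LOCF for these variables, since the model makes both unnecessary.

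The cost is a change of procedure within the same software and a less familiar output table. The substantive price is reliance on data being missing at random given the readings observed. Removals for hemodynamic instability could strain that assumption, so it should be stated, and the number of missing readings and the reasons reported by arm. The sample size does not change.
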